**Incremental Recovery:**

Recovery values according to the chromogenic assay were similar to measurements with the one-stage assay (see Table 18). Incremental Recovery analysis after 6 months of prophylactic treatment yielded comparable results with incremental recovery after the first dose (see Table 19).

**Table 18. Incremental Recovery in PTPs  $\geq$  12 Years of Age**

	Study 1	Study 2	Pooled Analysis
Study participants	N=59	N=56	N=115
Chromogenic assay results Median (Q1; Q3) (IU/dL per IU/kg)	2.5 (2.1; 2.8)	2.1 (1.7; 2.4)	2.3 (1.8; 2.6)
One-stage assay results Median (Q1; Q3) (IU/dL per IU/kg)	2.2 (1.9; 2.5)	2.1 (1.7; 2.3)	2.2 (1.8; 2.4)

**Table 19: Incremental Recovery in PTPs 0-12 Years of Age**

Study participants	Study 3	
	PTPs 0 to <6 yrs	PTPs 6 to 12 yrs
	N=24	N=25
Start of study: Chromogenic assay results Median (Q1; Q3) (IU/dL per IU/kg)	1.6 (1.3; 1.9)	1.7 (1.4; 2.0)
	N=23	N=25
After 6 months: Chromogenic assay results Median (Q1; Q3) (IU/dL per IU/kg)	1.8 (1.4; 2.0)	1.8 (1.1; 2.1)

**[Storage]**

KOVALTRY should be stored and transported at 2-8°C. Do not freeze.

Administer reconstituted KOVALTRY as soon as possible. If not, store at room temperature for no longer than 3 hours.

**[Package]**

- Packaging materials in direct contact with drug product: Type I glass vial, bromobutyl grey stopper
- A vial of recombinant coagulation factor VIII for injection
- A prefilled diluent syringe containing 2.5 ml of sterile water for injection
- A sterile vial adapter
- A single use administration set with filter

**[Shelf life]**

30 months

**[Executive Specification]**

Registration specification for imported drug JS20160071

**[Import Drug License No.]**

250 IU/vial: **CCI** [REDACTED]

500 IU/vial: **CCI** [REDACTED]

1000 IU/vial: **CCI** [REDACTED]

**[Hotline] [contact]**

**<Appendix: Preparation and Reconstitution>**

- Reconstitute and administer KOVALTRY with the components provided with each package. If any component of the package is opened or damaged, do not use this component.
- For any questions about the handling, reconstitution and administration of KOVALTRY, contact Bayer Medical Communications at Bayer [contact]).

[figure not shown]
[figure not shown]
[figure not shown]
The procedures below are provided as general guidelines for the reconstitution of KOVALTRY using the sterile vial adapter with a 15 micrometer filter and a prefilled diluent syringe, which together serve as an alternative needleless reconstitution system.

[figure not shown]
[figure not shown]
[figure not shown]
[figure not shown]
[figure not shown]
[figure not shown]
[figure not shown]
**Usability Testing of Vial Adapter**

Usability testing was conducted with 60 users, including 15 pediatric hemophilia A patients (between 10-17 years of age), 15 adult hemophilia A patients ( $\geq 18$  years of age), 15 caregivers, and 15 healthcare providers. To mimic real life, the pediatric and adult patients and the caregivers were given minimal training, which included participants performing a supervised reconstitution and later performing a single unaided reconstitution. Healthcare providers were untrained in this study and could learn the procedure from the provided Instructions for Use. All participants were able to successfully and safely use the vial adapter device for reconstitution.

**Reconstitution**

[figure not shown]
- Work on a clean surface and wash hands thoroughly using soap and warm water before performing the procedures.
- Reconstitute KOVALTRY with the components provided with each package. If any component of the package is opened or damaged, do not use this component.
- Filter the reconstituted product to remove potential particulate matter in the solution. Filtering is achieved by using the vial adapter.

1. Warm both unopened KOVALTRY vial and prefilled diluent syringe in your hands to a comfortable temperature (do not exceed 37°C or 99°F).	
2. Remove the protective cap from the vial (A). Aseptically cleanse the rubber stopper with a sterile alcohol swab, being careful not to handle the rubber stopper.	
3. Place the product vial on a firm, non-skid surface. Peel off the paper cover on the vial adapter plastic housing. Do not remove the adapter from the plastic housing. Holding the adapter housing, place over the product vial and firmly press down (B). The adapter will snap over the vial cap. Do not remove the adapter housing at this step.	
4. Holding the syringe by the barrel, snap the syringe cap off the tip (C). Do not touch the syringe tip with your hand or any surface. Set the syringe aside for further use.	

5. Now remove and discard the adapter plastic housing (D).	
6. Attach the prefilled syringe to the vial adapter thread by turning clockwise (E).	
7. Remove the clear plastic plunger rod from the carton. Grasp the plunger rod by the top plate. Avoid touching the sides and threads of the plunger rod. Attach the plunger rod by turning it clockwise into the threaded rubber stopper of the prefilled syringe (F).	
8. Inject the diluent slowly by pushing down on the plunger rod (G).	
9. Swirl vial gently until all powder on all sides of the vial is dissolved (H). Do not shake vial. Be sure that all powder is completely dissolved. Do not use if solution contains visible particles or is cloudy.	
10. Push down on the plunger to push all air back into the vial. Then while holding the plunger down, turn the vial with syringe upside-down (invert) so the vial is now above the syringe (I).	
11. Withdraw all the solution into the syringe by pulling the plunger rod back slowly and smoothly (J). Tilt the vial to the side and back to make sure all the solution has been drawn toward the large opening in the rubber stopper and into the syringe. Remove as much air as possible before removing the syringe from the vial by slowly and carefully pushing the air back into the vial.	

12. Detach the syringe with plunger rod from the vial adapter by turning counter-clockwise. Attach the syringe to the administration set provided and inject intravenously (K).

Note: follow instructions for infusion set provided.

#### Pooling

If the dose requires more than one vial, reconstitute each vial as described above with the diluent syringe provided. Use a larger plastic syringe (not provided) to combine the content of the vials into the syringe.

# Statistical Analysis Plan

BAY 81-8973 (KOVALTRY) / 19855

Page: 2 of 15

## Statistical Analysis Plan

BAY 81-8973 (KOVALTRY) / 19855

Page: 3 of 15

### Abbreviations

AE	Adverse event
CI	Confidence interval
CSR	Clinical Study Report
GCP	Good Clinical Practice
ICH	International Council for Harmonisation
MedDRA	Medical Dictionary for Regulatory Activities
N/A	Not applicable
PPS	Per-protocol set
SAE	Serious adverse event
SAP	Statistical Analysis Plan
AE	Adverse event
AUC	Area under the curve
BU	Bethesda unit
CL	clearance
C max	maximum concentration
dL	deciliter
CRF	Case Report Form
eCRF	Electronic Case Report Form
ED	exposure day
EPD	Electronic Patient Diary
FVIII	Factor VIII
IU	International Unit
IVR	in vivo recovery
kg	kilogram
LLOQ	lower limit of quantification
ITT	Intent-to-treat
ITI	Immune tolerance induction
MedDRA	Medical Dictionary for Regulatory Activities
MRT	mean residence time
n/a	not applicable
PDD	Protocol Deviations Document
PPS	Per-Protocol Analysis Set
PTP	previously treated patient
PUP	previously untreated patient
QoL	quality of life
rFVIII	recombinant Factor VIII
PP	Per-protocol
SAF	Safety Analysis Set
SAP	Statistical Analysis Plan
t 1/2	half-life
TLF	Tables, Listings, Figures
V ss	steady state volume

## Statistical Analysis Plan

BAY 81-8973 (KOVALTRY) / 19855

Page: 4 of 15

### 1. Introduction

This statistical analysis plan (SAP) version 2.0 is based on the finalized Protocol Version 2.0, dated 22 OCT 2020.

The protocol version 2.0, dated 22 OCT 2020 is integration of the original protocol version 1.0, dated 29 Jan 2020 and the amendment 1.

This SAP describes the study objective, study design, analysis sets, all endpoints, and statistical analysis methods. Complete details of Tables, Listing and Figures (TLFs) specifications as well as dataset details and data handling specifications will be provided in separate “TLF specifications” and “Analysis Datasets” documents as an integral part of this SAP.

### 2. Study Objectives

#### 2.1 Study Objectives – Part A (PTPs)

##### Primary objective

- Evaluate the efficacy of prophylaxis treatment with KOVALTRY in previous treated Chinese children (<12 years) and adolescents/adults ( $\geq 12$  years) with severe hemophilia A.

##### Secondary objectives

###### Efficacy

- Evaluate efficacy of KOVALTRY for treatment of bleeding episodes
- Assess efficacy within 48 hours of previous prophylaxis infusion
- Evaluate the in vivo recovery of KOVALTRY
- Hemostatic control for minor surgeries

###### Safety

- Assess the safety of KOVALTRY for prophylaxis and treatment of bleeding episodes in Chinese children (<12 years) and adolescents/adults ( $\geq 12$  years) with severe hemophilia A.

###### Pharmacokinetic

- Evaluate pharmacokinetics (PK) of KOVALTRY in Chinese children (<12 years) and adolescents/adults ( $\geq 12$  years to 65 years) severe hemophilia A patients.

#### 2.2 Study Objectives – Part B (PUPs)

##### Primary objective

- Evaluate the efficacy of KOVALTRY within 48 hours of previous prophylaxis infusion in previously untreated/ minimally treated Chinese children (<6 years of age) with severe hemophilia A.

## Statistical Analysis Plan

BAY 81-8973 (KOVALTRY) / 19855

Page: 5 of 15

### Secondary objectives

#### Efficacy

- Evaluate efficacy of prophylaxis treatment with KOVALTRY
- Assess the efficacy of KOVALTRY for treatment of bleeding episodes
- Evaluate the in vivo recovery of KOVALTRY
- Hemostatic control for minor surgeries

#### Safety

- Assess the safety of KOVALTRY for prophylaxis and treatment of bleeding episodes in previously untreated/minimally treated Chinese children (<6 years of age) with severe hemophilia A.

## 3. Study Design

This is a multicenter, uncontrolled open-label, two group treatment study to assess efficacy, safety and PK of KOVALTRY in previously treated Chinese children and adolescents/ adults with severe hemophilia A.

### Part A (PTPs)

Part A will assess the efficacy, safety, and PK of KOVALTRY in previously treated Chinese children and adolescents/adults with severe hemophilia A. Part A is planned to investigate a total of 42 PTPs (30 children and 12 adolescents/adults). PK will be assessed in a subset of 12 children (<12 years) and in 12 adolescents/adults ( $\geq 12$  years).

Efficacy and safety data for use of KOVALTRY for treatment of bleeding episodes will also be collected.

- Study participants will be treated for 6 months with the following dose regimen for prophylaxis according to the prescribing information for KOVALTRY:
  - Study participants  $\leq 12$  years of age: 25 to 50 IU of KOVALTRY per kg body weight twice weekly, three times weekly, or every other day according to individual requirements for 6 months.
  - Study participants  $> 12$  years: 20 to 40 IU of KOVALTRY per kg of body weight two or three times per week according to individual requirements for 6 months.
- Part A will include 5 study visits (Screening, Baseline, Visit 3/Month 1, Visit 4/ Month 2, Visit 5/Final study visit/Early Termination). All participants will also receive a safety follow-up call approximately 2 weeks after the final study visit.

### Part B (PUPs)

Part B will assess the efficacy and safety of KOVALTRY in previously untreated/minimally treated Chinese children with severe hemophilia A. Part B will investigate approximately 6 PUPs/MTPs.

Efficacy and safety data for the use of KOVALTRY for treatment of bleeding episodes will also be collected.

- Study participants will be treated until at least 50 ED is achieved.

## Statistical Analysis Plan

- Treatment may begin with start of prophylaxis with 15 to 50 IU/kg (minimum dose: 250 IU) at least 1 day a week; alternatively, prophylaxis can be started directly with a once-a-week schedule minimum dose of 250 IU for PUPs/MTPs of any weight.
- The starting dose may be tailored to the participant's weight or demonstrated bleeding tendency.
- Individual participant dose decisions are at the discretion of the investigator.
- Part B will include 8 study visits (Screening, Baseline [may be combined with the Screening visit for PUPs], Visit 3 [approximately 5 ED], Visit 4 [approximately 10 ED], Visit 5 [approximately 15 ED], Visit 6 [approximately 20 ED], Visit 7/Interim visit [approximately 30 to 40 ED], and Visit 8/Final visit [50 ED]/Early Termination). All parents/caregivers of participants in Part B will receive a safety follow-up call approximately 2 weeks after the end of treatment.

### 3.1 Sample size determination

#### 3.1.1 Part A (PTPs)

The primary variable “annualized bleeding rate (ABR)” is used for the evaluation of the efficacy. The mean ABR for total bleeding episodes for previously treated severe hemophilia A study participants < 12 year of age receiving prophylaxis with KOVALTRY in completed LEOPOLD Kids Part A study was  $3.75 \pm 4.98$  (median (Q1; Q3) 1.90 (0.00; 6.02). Assuming that the average ABR for this patient population is 4 bleeding episodes and the standard deviation is 5 bleeding episodes per year, a sample size of 30 participants will allow estimating ABR by means of a 95% confidence interval with a half-width of 1.8 (the confidence interval is (2.2-5.8) which will consider to provide reasonable precision on the estimations.

For the previously treated adult/adolescent treatment arm, the proposed sample size of 12 participants is adequate for collection of PK data and will also allow for collection of supplemental efficacy and safety data in this population.

The sample size (30 children + 12 adolescents and adults) has been confirmed in consultation with China CDE, as adequate to provide additional clinical data for comprehensive evaluation of efficacy, safety, and PK of KOVALTRY in Chinese hemophilia A patients.

#### 3.1.2 Part B (PUPs)

To fulfill the post-approval commitment enforced for KOVALTRY, the Sponsor is committed to collecting additional efficacy and safety data in previously untreated Chinese severe hemophilia A patients, in line with the CDE Technical Guideline on the Clinical Investigation of Recombinant Human Coagulation Factor VIII.

It is considered feasible to enroll approximately 6 PUPs/MTPs in Part B of this study.

Part B of this study is designed in accordance with the multinational clinical trial of KOVALTRY in previously untreated/minimally treated patients, LEOPOLD Kids Part B, where the annualized number of bleeds that occur within 48 hours after a prophylaxis infusion was the primary efficacy endpoint.

A mean of 1.9 (standard deviation 3.3) was observed for this ABR in LEOPOLD Kids Part B. Assuming the same distribution, the point estimate for the ABR within 48 hours after a prophylaxis infusion of 6 patients will be smaller than 2.9 with a probability of more than 80% (based on simulations of data for 6 patients from a negative binomial distribution).

In addition, in the SIPPET study (a multinational, prospective, randomized trial that assessed the incidence of FVIII inhibitors among PUPs treated with plasma-derived FVIII containing von

## Statistical Analysis Plan

BAY 81-8973 (KOVALTRY) / 19855

Page: 7 of 15

Willebrand factor or rFVIII products), the incidence of inhibitor development for the class of rFVIII products was 44.5% (95% CI: 34.7% to 54.3%).

Therefore, the true inhibitor rate for PUPs/MTPs is assumed to be within the range of 35% to 54%. With a sample size of 6 PUPs/MTPs, there is at least 92% power to observe at least 1 participant developing an inhibitor if the rate is between 35% and 54%. In case an event of inhibitor development is not observed, this sample size would provide more than 90% reassurance that the inhibitor rate should be no more than 35%.

### 4. General Statistical Considerations

#### 4.1 General Principles

There is no confirmatory comparison planned for this study, study results will be numerically evaluated.

Part A and Part B will be analyzed separately, both for efficacy and safety. The optional ITI treatment period will only be considered for the safety analysis.

The efficacy and safety analysis will be presented as summary statistics by age groups (<12 or  $\geq 12$  years of age) in Part A.

The statistical evaluation will be performed by using the software package SAS release 9.2 or higher (SAS Institute Inc., Cary, NC, USA). All variables will be analyzed by descriptive statistical methods. The number of data available and missing data, mean, standard deviation, minimum, quartiles, median, and maximum will be calculated for metric data. Frequency tables will be generated for categorical data.

#### 4.2 Handling of Dropouts

Annualized number of total bleeds will be calculated for all subjects, including dropouts. Subjects who drop from the study will be included in a listing.

During the study, temporary discontinuation of study drug could happen, the duration of interruption of study intervention (i.e. prophylaxis treatment with KOVALTRY) should not be more than 2 weeks. Prolonged periods ( $> 2$  weeks) or repeated breaks in the prophylaxis schedule should be avoided and could result in the study participant treated as drop out, or being removed from the study.

#### 4.3 Handling of Missing Data

All missing or partial data will be presented in the subject data listing as they are recorded on the Case Report Form (CRF).

*Missing or incomplete AE start and end date or time:*

For the purpose of treatment emergent flags, missing AE start day will be imputed as the 15th of the month. However, if the AE start day is missing, but the AE starts during the same month as the first dose, or if the AE starts on the same day as the first dose, but the AE start time is missing, the AE start day (and time in the second case) will be taken from first dose start day (and time). If both day and month of AE start date are missing, day and month will be imputed as July 1st, or the date of the first dose, whichever comes later.

Drug-related AE tables will include AEs with missing values of causality.

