#### 6.4.2 Adverse events

Individual listings of AEs (including age, AEs as reported, start, duration, severity, relation to study drug) will be provided.

For each AE, the number and percentage of subjects who experienced at least 1 occurrence of the AE will be tabulated according to the primary system organ class (SOC) and preferred term (PT) by age groups and overall study population combined.

Frequency tables, showing the number of subjects with drug-related AEs, SAEs, AE related to deaths, AE resulting in permanent discontinuation of study drug, and AESIs will be given.

An AE is defined as treatment-emergent if it started or deteriorated after the first infusion and not later than three days after the last infusion. The incidence of treatment-emergent AEs will be summarized using the Medical Dictionary for Regulatory Affairs (MedDRA).

Determination of whether or not an event is treatment-emergent will be derived after the missing or incomplete AE start date is imputed. In case an adverse event starts on the day of first administration of study drug and the time of onset is not known, the event is considered to be not treatment emergent, if it is reported to occur before the first dose of study drug. Details about imputation rules for missing and incomplete AE start are described in section 4.3.

In all other cases the event is considered to be treatment emergent. Inhibitors will be defined as treatment-emergent if they develop after first study drug application.

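### The imputed AE start date has no upper bound, so partly dated events near the end of treatment are misclassified as treatment-emergent or not, in both directions

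*SAP*

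**What the plan says.** SAP 4.3 gives two rules for incomplete AE start dates, for the purpose of the treatment-emergent flag. If only the day is unknown, "missing AE start day will be imputed as the 15th of the month". If day and month are unknown, "day and month will be imputed as July 1st, or the date of the first dose, whichever comes later". The only adjustments are at the start of treatment: an event in the month of first dose, or on the day of first dose with time unknown, takes the first-dose date or time. Nothing limits the imputed date by the last infusion, the AE end date or the last contact.

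SAP 6.4.2 counts an AE as treatment-emergent if it starts or worsens after the first infusion and "not later than three days after the last infusion". Protocol 9.4.4 uses the same window. SAP 6.4.2 also fixes the order of steps: "Determination of whether or not an event is treatment-emergent will be derived after the missing or incomplete AE start date is imputed".

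Two further sentences in SAP 6.4.2 matter. After the case of an event on the first-dose day with unknown time, it says "In all other cases the event is considered to be treatment emergent". It then says "Inhibitors will be defined as treatment-emergent if they develop after first study drug application", with no three-day limit.

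**The concern.** The start of the treatment window is protected against imputation error and the end is not. Because the flag is computed after imputation, the choice of the 15th or of 1 July can by itself decide whether an event counts. It can also give a start date after the participant's last contact, which is impossible for an event collected only up to the follow-up call (Protocol 8.4.1).

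Treatment-emergent AEs are a named safety endpoint in both parts (Protocol 3.1 and 3.2). The groups are small: 30 children, 12 adolescents/adults and about 6 participants in Part B. If the misclassified event is a participant's only such event, the incidence moves by 1/30 = 3.3, 1/12 = 8.3 or 1/6 = 16.7 percentage points. Imprecise dates are plausible at the end of Part A, because events after the final-visit infusion are asked about by telephone roughly two weeks later (Protocol 7.1.5 and 7.1.6).

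**Working it through.** The documents give no figure for this point, so there is none to reproduce. The check enumerates calendar dates.

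**Inputs**
- Imputed dates: the 15th, or the later of 1 July and first dose (SAP 4.3).
- Cut-off: last infusion + 3 days (SAP 6.4.2).
- Part A duration: "Study participants will be treated for 6 months" (SAP 3), taken as 183 days, with 176 and 190 for the ±7-day visit window.
- Last infusion: at the final visit (Protocol 7.1.5).
- Last contact: 7 to 21 days after the final visit, planned at 14 (Protocol 7.1.6).
- Assumption: last-infusion days and onset days are spread evenly over the calendar.

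**1. Day missing, event in the month of last infusion (not the first-dose month)**

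Let d be the calendar day of the last infusion. The event is flagged emergent only if 15 ≤ d + 3, that is, d ≥ 12. For d = 1 to 11 it is always flagged non-emergent. That is 11/31 = 35%, 11/30 = 37% or 11/28 = 39% of possible last-infusion days.

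*Wrongly excluded.* For d = 1 to 11, the truly emergent onset days in the month number d + 3. Their sum is 66 + 33 = 99. The total of truly emergent positions is the sum of min(L, d + 3) over all d in a month of L days:

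| Month length | Wrongly excluded / truly emergent | Share |
|---|---|---|
| 28 | 99/484 | 20.5% |
| 30 | 99/549 | 18.0% |
| 31 | 99/583 | 17.0% |

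Example: last infusion 5 September, cut-off 8 September, true onset 2 September, imputed 15 September, so not treatment-emergent.

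*Wrongly included.* For d ≥ 12, onsets from d + 4 up to last contact or month end are imputed to the 15th and counted. In a 30-day month with the call at 14 days, d = 12 to 16 give 5 × 11 = 55 and d = 17 to 26 give 10 + 9 + … + 1 = 55, so 110 of 231 non-emergent positions. With the call at 7 or 21 days the counts are 54 of 98 and 120 of 315.

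*Net.* If the last infusion is on day 28, 29 or 30 of a 30-day month, a further 1 + 2 + 3 = 6 truly emergent positions fall in the next month and are imputed to its 15th. The balance at the planned call is 99 + 6 = 105 wrongly excluded against 110 wrongly included.

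*Scale over the whole treatment.* On average 105/30 = 3.5 onset days are affected out of 183 + 3 = 186, about 1.9% of truly emergent day-missing events if onset is even over treatment.

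**2. Day and month missing, Part A**

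With 183 days, a participant first dosed from 2 July to 31 December (183 dates) has his last infusion in the next calendar year. An event dated only to that second year is imputed to 1 July.
- 1 July is later than last infusion + 3 days for first doses from 2 July to 26 December: 178 of 183 dates. At 176 days it is 176 of 176; at 190 days, 178 of 190.
- 1 July is later than the latest possible call (+21 days) for 160 first-dose dates at each duration.
- Example: last infusion 1 March 2022, event dated 2022, imputed 1 July 2022, which is 122 days after the last infusion.

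In the first-dose year, completers are almost unaffected (0 to 2 of 365 dates). Early terminators can be affected: with 90 days of treatment, first doses from 1 January to 29 March (88 dates) are imputed past the cut-off. In the other direction, a year-only event that began during screening in the first-dose year is imputed to first dose or later and can be counted as emergent.

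**3. With the change proposed below**

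In a 30-day month, wrongly excluded in-month positions fall from 99 to 0. Wrongly included in-month positions at the 14-day call rise from 110 to all 231. Second-year year-only exclusions fall from 178 of 183 dates to 0.

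**The case against.** The strongest reply is that little depends on this. The study is single-arm and descriptive. Participants are called about every two weeks to review new events, start and stop dates are to be recorded, and source data are verified, so year-only dates should be rare. Partial dates are listed as recorded and every AE is listed. Inhibitor development, the most important risk, is outside the three-day limit. All of this stands and keeps the point minor.

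A second reply is that the sentence "In all other cases the event is considered to be treatment emergent" rescues these events. It follows the first-dose-day case. Read as a general rule, it would cancel the three-day limit stated in the same section. It is an ambiguity to clear up rather than a safeguard.

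A third is that SAP 1 places data handling details in separate specifications. Those are not available here, and they cannot be assumed to override explicit SAP text.

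A reader might also infer that the rule biases treatment-emergent counts downward in general. The figures do not support that for missing days, where 105 exclusions stand against 110 inclusions. Nor is the 35 to 39% of last-infusion days an error rate. It is the share of end dates on which a wrong exclusion is possible, and events that truly began after the cut-off are correctly excluded on those days.

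**Conclusion.** The point holds as a minor defect. SAP 4.3 and 6.4.2 together give wrong flags for partly dated events near the end of treatment and can place an onset after last contact. For missing days the rule errs in both directions: it loses 17 to 20% of truly emergent day-missing events in the month of last infusion, and wrongly counts a similar number of later ones. Only the year-only rule in the second calendar year of Part A is clearly downward (178 of 183 first-dose dates, 160 of them past the latest call).

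These figures assume evenly spread dates and, for the year-only case, a six-month treatment ending with the final-visit infusion. They are conditional on an event being partly dated. The documents give no rate for that, so no effect on the reported incidence can be stated.

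**What to change.** In SAP 4.3:
- Flag an AE as treatment-emergent unless the known parts of its start date show onset before the first dose or more than three days after the last infusion.
- Never impute a start later than the AE end date or last contact, and never move it outside the recorded month or year. An unconditional cap at the last infusion would break this: after a last infusion on 20 August, it would move an event recorded in September back to August.

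In SAP 6.4.2, state which cases "In all other cases the event is considered to be treatment emergent" covers.

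The cost is a few lines of text. SAP 2.0 is based on protocol version 2.0 and the current protocol is version 4.0, so the edit could go with an alignment update. The statistical price is that some partly dated events that began after the window will be counted as treatment-emergent, which is the conservative direction for safety.
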